## **7.4. Handling of Missing Data**

The handling of missing data and appropriate imputations described in the following sections will be performed after all efforts fail to obtain the data.

If appropriate, retrieved data will be used. A retrieved assessment is one collected after the early discontinuation of ALIS/ELC; a retriever is a subject who stays in the study and continues to provide data after discontinuation of the randomized treatment regimen.

### **7.4.1. Missing PRO Administrations and Missing Item Responses**

Missing individual PRO items will not be imputed. Missing PRO items will be very rare given the ePRO collection procedures.

Domain scores will be calculated as described within the corresponding variable section. In cases when the domain score is derived, derivation will follow the rules specified for missing data handling described within the corresponding efficacy section.

The imputation details of this data are described in [Section 9.3.2.2](#) and [Appendix I](#).

### **7.4.2. Missing Culture Conversion Assessments**

Handling missing microbiological results is described in the protocol Section 8.1 and SAP [Section 9.3.1](#).

Missing data that resulted from early termination of therapy has the same reasons as those described for the PRO. The imputation details of this data are described in [Appendix I](#).

### **7.4.3. Missing Start and Stop Dates for Prior and Concomitant Medication**

The rules to categorize medications as 'Prior' and/ or 'Concomitant' are described in [Section 12.14](#). There is no need to impute missing or partially missing start or stop dates.

### **7.4.4. Missing Start and Stop Dates for Adverse Events**

The rules to categorize AEs to 'TEAE' or 'non-TEAE' are described in [Section 12.4](#). There is no need to impute missing or partially missing start or stop dates.

### 7.4.5. Missing Dates Drug Interruption

Missing end date of drug interruption will be imputed by date of EOT or EOS whichever comes first.

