4.2. Discontinuation of Study Drugs and Participant Discontinuation/Withdrawal

4.2.1. Discontinuation of Study Drugs

All subjects are encouraged to stay in the study for continued safety monitoring regardless of discontinuation of study drugs. If a subject discontinues one or more study drugs (ALIS/ELC, AZI, and/or ETH), they will remain on the other study drug(s) and continue with the scheduled study visits. For these subjects, it is highly encouraged to stop all MAC treatment at Month 6 (per study design) to evaluate the primary and secondary endpoints during the off treatment period. However, if deemed medically necessary per the Investigator, these subjects who prematurely discontinue one or more study drugs may be allowed to continue treatment during the off treatment period.

If a subject discontinues ALIS or ELC:

- The reason for ALIS or ELC discontinuation will be recorded in eCRF.
- The subject will remain on the other study drugs (AZI and ETH) and continue with the next scheduled study visit.
- At the next scheduled visit, the subject will complete the EOT visit assessments.
- The subject will complete a Month 6 visit when they reach Month 6.

If a subject discontinues AZI and/or ETH, the reason for drug discontinuation should be recorded in the eCRF. The EOT visit should not be completed at this time. The subject will remain on the other study drugs (ALIS/ELC and AZI or ETH) and should initiate therapy consistent with the 2020 ATS/ERS/ESCMID/IDSA treatment guidelines ([Daley et al., 2020](#)), and continue with the next scheduled study visit. Any changes to therapy and treatment regimen should aim to prevent the development of macrolide resistance. Changes to treatment should be discussed with the Medical Monitor to ensure compliance with the 2020 ATS/ERS/ESCMID/IDSA treatment guidelines.

For subjects who discontinue one or more study drugs, replacement therapy may be provided at the discretion of the Investigator; this is not considered rescue therapy.

Subjects may be discontinued from one or more study drugs at the discretion of the Investigator if they meet treatment stopping criteria per local labeling guidance.

If a subject withdraws consent from continued safety monitoring, the EOS visit should be completed.

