## 2. INTRODUCTION

The purpose of this SAP is to describe the planned analyses to be included in the CSR for study INS-415.

The reader is encouraged to read the study protocol for details on the conduct of this study, the operational aspects of clinical assessments, and the timing for a subject to complete participation in this study.

The SAP is intended to be in agreement with the protocol. However, the SAP may contain more details or other types of analyses (eg, other endpoints). When differences exist in descriptions or explanations provided in the study protocol and this SAP, the SAP prevails; the differences will be explained in the CSR.

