### Treatment Period

The treatment period starts with the first dose of ALIS/ELC, AZI and/or ETH.

The end of treatment (EOT) is defined as the date of the last dose of ALIS/ELC, AZI and/or ETH whichever study drug dose is taken last.

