### 12.1. Treatment and Study Duration

- 1) Duration of treatment will be summarized descriptively; separately for each study drug [ALIS/ELC, AZI, ETH] and for all study drugs combined.

$$\text{duration of treatment (days)} = \text{date of last dose} - \text{date of first dose} + 1$$

This definition does not account for protocol-allowed interruptions.

- 2) Study drug exposure will be summarized descriptively; separately for each study drug [ALIS/ELC, AZI, ETH] and for all study drugs combined.

$$\begin{aligned} \text{duration of exposure (days)} = \\ \text{date of last dose} - \text{date of first dose} + 1 - \text{total number of days with protocol-} \\ \text{prescribed prescribe interruptions due to safety reasons} \end{aligned}$$

For all study drugs combined the derivation is

$$\begin{aligned} \text{duration of exposure (days)} = \\ \text{date of last day all study drugs are concurrently administered} - \\ \text{date of first day all study drugs are concurrently administered} + 1 - \\ \text{total number of days any study drug was interrupted due to safety reasons} \end{aligned}$$

- 3) The duration of study will be calculated as number of days between randomization and end of study and summarized descriptively.

$$\text{duration of study (days)} = \text{end of study date} - \text{date of randomization} + 1$$

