**Table 9: Changes to Protocol-Specified Analyses**

Revision	Protocol Section	SAP Section	Rationale
End of treatment	3.4: "The EOT is defined as the date when the EOT visit occurs."	4.2: "The end of treatment (EOT) is defined as the date of the last dose of ALIS/ELC, AZI and/or ETH whichever study drug dose is taken last."	The definition clarifies the possibility of different study drugs discontinuation dates.

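### A missing interruption end date is filled with the last dose of any study drug and then deducted from the interrupted drug's own dosing span, so exposure can be understated or negative

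*SAP*

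**What the plan says.** - **Imputation (SAP 7.4.5).** "Missing end date of drug interruption will be imputed by date of EOT or EOS whichever comes first". The rule is the same for all drugs and does not ask whether the interrupted drug was taken again.
- **EOT (SAP 4.2, Treatment Period).** EOT is "the date of the last dose of ALIS/ELC, AZI and/or ETH whichever study drug dose is taken last". SAP Table 9 lists this as a change from the protocol's EOT visit date, with the reason: "The definition clarifies the possibility of different study drugs discontinuation dates". SAP section 2 settles precedence: "When differences exist in descriptions or explanations provided in the study protocol and this SAP, the SAP prevails".
- **Exposure per drug (SAP 12.1, item 2).** Last dose minus first dose plus 1, less the days with protocol-"prescribed prescribe interruptions due to safety reasons". There is no floor at zero and no limit to that drug's dosing span.
- **Exposure for all drugs combined (SAP 12.1, item 2).** The span in which all drugs are given together, less the "total number of days any study drug was interrupted due to safety reasons".
- **Which interruptions count (SAP 12.3).** Every reported interruption is treated as a protocol-allowed safety interruption, so none escapes the deduction.
- **After ALIS/ELC is stopped (Protocol 4.2.1).** "The subject will remain on the other study drugs (AZI and ETH) and continue with the next scheduled study visit".

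**The concern.** The two terms of the exposure formula run on different clocks. The first ends at the last dose of the drug in question. The second, when an end date is missing, can run to the last dose of a different drug. Protocol 4.2.1 keeps a subject on AZI and ETH after ALIS/ELC stops, so the two dates can be months apart, and the formula then deducts days it never counted.

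A second problem arises when the drug was resumed and only the end date is missing. Every later dosing day is then treated as off drug. SAP 12.2 sets the expected units on those days to 0, while the units used still come from drug accountability.

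At stake are the exposure tables, the interruption-length summary in SAP 12.3 and, for resumed subjects only, the compliance categories.

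**Working it through.** The documents state no exposure figure to reproduce, so the check is date arithmetic on the SAP's own formulas.

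**Inputs**
- Treatment length: 6 months at 28 days per month (SAP 7.6.1) = 168 days.
- Assumed for illustration: first dose of all drugs on Day 1; AZI/ETH to Day 168, so EOT = Day 168; EOS visit about Day 196 (7 x 28). The earlier of EOT and EOS is Day 168.

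**Case 1: not resumed.** Last ALIS/ELC dose on Day L; interruption recorded from Day L + 1 with no end date.
- Own dosing span: L - 1 + 1 = L days.
- Imputed interruption: 168 - (L + 1) + 1 = 168 - L days.
- Exposure: L - (168 - L) = 2L - 168.

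| L | Days deducted | Exposure as written | Own dosing span |
|---|---|---|---|
| 30 | 138 | -108 | 30 |
| 60 | 108 | -48 | 60 |
| 83 | 85 | -2 | 83 |
| 84 | 84 | 0 | 84 |
| 120 | 48 | 72 | 120 |

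Exposure is negative whenever L is below half of EOT: up to Day 83 for EOT Day 168, Day 89 for EOT Day 180 and Day 91 for EOT Day 183. A later stop gives a positive but understated value.

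**Case 2: combined measure, same subject.** With L = 60, all drugs are given together on Days 1 to 60, and 108 days are deducted: 60 - 108 = -48. Here the defect does not even need a missing date. A fully dated AZI or ETH interruption after the last ALIS/ELC dose is also deducted from a window that had already closed.

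**Case 3: resumed, end date missing.** True gap Days 30 to 36 (7 days); dosing then continues to Day 168.
- Imputed interruption: 168 - 30 + 1 = 139 days, against 7.
- Exposure: 168 - 139 = 29 days, against 168 - 7 = 161.
- Compliance (SAP 12.2): 161 daily doses used over 29 expected = 555%, so a fully compliant subject falls in the category above 120%.

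**Compliance in Case 1.** Expected units run only from that drug's first dose to its last, so the imputed days after the last dose have no effect.

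**If EOT is read as the protocol's EOT visit.** Last dose Day 30 with the next in-clinic visit on Day 84: 30 - (84 - 30) = -24. With a Day 56 visit: 30 - 26 = 4. The problem shrinks but remains.

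**The case against.** **EOT may mean the drug's own last dose.** SAP 12.2 and the footnote to Table 6 take a drug-specific last dose from the End of Treatment form. If SAP 7.4.5 meant that date, the deduction in Case 1 would be zero and the negative value would vanish. But those places refer to a form. The formal definition in SAP 4.2, repeated in Table 9, is the last dose of any drug. The alternative reading would not rescue Case 3 either, because there the drug's own last dose is still Day 168.

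**The situation may be rare.** This stands. SAP 7.4 allows imputation only after efforts to obtain the data have failed. Protocol 4.2.1 records the reason for ALIS/ELC discontinuation separately, and Protocol 5.1.4.1 presents interruption as a way to avoid stopping. Nothing says that a stopped drug leaves an open interruption record, though nothing rules it out.

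**Correct figures sit beside the wrong ones.** This also stands. Treatment duration (SAP 12.1, item 1) has no interruption deduction. Exposure-adjusted incidence rates (SAP 12.4) use time at risk built from first and last dose dates. All summaries are descriptive (SAP 7.2).

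**Running an unresumed interruption to EOT is a fair description of its length.** Agreed for SAP 12.3. In Case 1 the fault lies in the deduction in SAP 12.1 rather than in the imputed date.

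**A stronger reading.** A reader might infer that open end dates usually mean the drug was never resumed, so that ALIS exposure will be understated against ELC and the tolerability assessment biased. The documents give no frequency of open records, no reason for them and no difference between arms, so they do not support that inference.

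**Conclusion.** The rule is wrong as written. Taken together, SAP 7.4.5, 4.2 and 12.1 can produce impossible exposure values (-48 days for a last ALIS/ELC dose on Day 60) and, for a resumed drug, 29 days instead of 161 with 555% compliance. These figures rest on a 168-day treatment period, the illustrative dates above and a literal reading of EOT as SAP 4.2 defines it.

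The practical size is unknown, because the number of affected subjects cannot be determined from the documents. For scale only, one subject with the Day 60 pattern would lower the mean of a 50-subject arm by 108/50 = 2.2 days.

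This is a minor error confined to descriptive exposure, interruption length and, for resumed subjects, compliance. It does not reach treatment duration, exposure-adjusted adverse event rates, efficacy or the psychometric validation.

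**What to change.** 1. **SAP 12.1, per drug:** deduct only interruption days that fall between the first and last dose of the same drug.
2. **SAP 12.1, combined:** deduct only days inside the window in which all drugs are given together.
3. **SAP 7.4.5, drug taken again after the interruption start:** impute the end date as the day before the first recorded later intake of that drug, from the eDiary or eCRF.
4. **SAP 7.4.5, drug not taken again:** keep the EOT/EOS imputation for the length summary in SAP 12.3 and flag the interruption as not resumed. The limit in item 1 then prevents the deduction.

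Items 1 and 3 are both needed. With item 1, the Day 60 subject gets 60 days, and no unresumed case can go negative. Item 1 alone leaves the resumed subject at 29 days; item 3 restores 161 days and compliance of 161/161 = 100%.

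Simply capping the imputed end date at the drug's own last dose is not a good substitute. With the interruption starting on Day 61 and ending on Day 60, SAP 12.3 would report 60 - 61 + 1 = 0 days for a drug that was stopped.

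The cost is a few sentences of SAP text and a small programming change. Last-dose dates are already collected for each drug. The eDiary records study drug intake, but the documents do not say whether it does so by drug and day, hence the eCRF as an alternative source.

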## 7.5. Intercurrent Events

The ICEs are defined as post-randomization events that occur after the study intervention has been initiated and which either precludes the observation of the outcome variable or affects its measurement or interpretation. This study identified ICEs as those leading to early ALIS/ELC therapy termination due to death, treatment (ALIS/ELC) related TEAE, use of rescue medication, or lack of efficacy.

When appropriate, efficacy analyses for secondary endpoints will be evaluated taking ICEs into consideration allowing a more precise estimation. Details on handling data after ICE occurred together with justification are provided in [Section 9](#).

## 7.6. Derived and Transformed Data

### 7.6.1. Durations

A duration between one date (*date1*) and another later date (*date2*) is calculated using the following formula:

- Duration (days) =  $date2 - date1 + 1$
- Duration (weeks) = duration (days) / 7
- Duration (months) = duration (days) / 28
- Duration (years) = duration (days) / 365.25

### 7.6.2. Study Day

Study Day associated with an event is calculated as the date of the event minus the date of first exposure to ALIS/ELC, ETH, or AZI (whichever is first) plus one (1) if the date of event is on or after the date of first exposure to study treatment.

If the date of event is before the date of first exposure to study treatment, the Study Day will have negative values and is calculated as the date of event minus the date of first exposure to study treatment.

Consequently, there is no Study Day 0.

### 7.6.3. Off-Treatment Day

The Off-Treatment Day is calculated as the date of event minus the date of last dose of study drugs if the date of event is on or after the date of last dose of study drugs. If the date of event is before the date of last dose of study drugs, Off-Treatment Day is set to missing.

On the date of last exposure to study drugs Off-Treatment Day will be 0.

#### 7.6.4. Multiple Assessments

Unless otherwise stated, if a subject has more than one numeric laboratory record for a specific parameter of interest at a specific visit and/or timepoint for any reason, the average of those specific data at that visit and/or timepoint will be considered in summary tables. Repeated values within a visit or timepoint will be listed individually.

If results are provided from both local and central laboratories, the central assessment will be used for reporting purposes.

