## 7. GENERAL STATISTICAL CONSIDERATIONS

### 7.1. General

All summaries will be provided by treatment group; efficacy analyses will utilize randomized treatment (ITT analysis set), while safety will use treatments as received (Safety analysis set).

In case of misrandomization to incorrect strata, subjects will be analyzed as collected in CRF.

Methods of cross-sectional analyses and psychometric validation of PRO are described in the VAP.

Descriptive statistics for continuous variables include n, mean, SD, median, minimum, maximum, 1st quartile and 3rd quartile. Summaries of continuous variables that have some values recorded using approximate values (eg, < or >) will use the numeric part of the value in calculations. Listings will present the data in its original format.

Categorical variables will be tabulated by counts and by percentage of subjects in corresponding categories. Footnotes will specify the basis for the percentages. Category including missing assessments will be included if appropriate.

Data from unscheduled visits will not be used in summaries, except for the derivation of baseline and the summary of subjects with an abnormal laboratory value.

Listings corresponding to all summaries in this section will be provided. Listings will also include data from unscheduled visits.

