#### 9.3.6. Microbiology Assessment

Mycobacteria isolate species (*Mycobacterium avium* complex overall, *M. avium*, *M. intracellulare*, and other speciated and unspciated MAC) are the variables of interest.

Drug susceptibility of MAC treatment will also be presented.

MIC ( $\mu\text{g/mL}$ ) is reported in powers of 2, eg,  $0.125 = 2^{-3}$ ,  $0.25 = 2^{-2}$ , ... ,  $64 = 2^6$ , etc. Therefore, the values that may appear in this table are 0.125, 0.25, 0.5, 1, 2, 4, 8, 16, 32, 64, 128 and >128. The MIC will be tabulated for each reported MIC value including any values not reported between the minimum and maximum values.

If there are multiple assessments collected for MIC assessment for one visit, the maximum MIC value will be used.

All variables will be tabulated by treatment (individual and overall) at each timepoint.

The denominator for percentages will be the number of subjects with available data.

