## 12.9. Clinical Laboratory Evaluations

Numeric laboratory parameters (hematology, chemistry (incl CRP), and urinalysis) will be summarized using descriptive statistics at baseline and at each post-baseline timepoint for the safety analysis set. Changes from baseline will also be summarized. Descriptive statistics at baseline and change from baseline is limited to continuous data.

Shift tables (ie, low-normal-high at baseline versus low-normal-high at follow-up in a 3-by-3 contingency table) will be provided to assess changes in laboratory values from baseline to post-baseline visits. Reference ranges established by the central laboratory will be used to determine shifts.

Clinical laboratory results will be provided in subject listings for the safety analysis set. Subjects experiencing ALT or AST  $\geq 3 \times$  ULN and total bilirubin  $> 2 \times$  ULN according to Hy's Law will be listed.

A summary of counts of subjects with an abnormal laboratory value at any visit including unscheduled will also be provided.

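### Averaging same-visit laboratory repeats can turn a modest abnormal result into a normal one in the shift tables, and the SAP does not say whether abnormal-value counts use averages or individual values

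*SAP*

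**What the plan says.** SAP 7.6.4 (Multiple Assessments) sets a default that holds unless the SAP states something else. It applies when a subject has "more than one numeric laboratory record for a specific parameter of interest at a specific visit and/or timepoint for any reason", and then "the average of those specific data at that visit and/or timepoint will be considered in summary tables". Listings are treated differently: "Repeated values within a visit or timepoint will be listed individually". Where local and central results both exist, the central one is reported.

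SAP 12.9 (Clinical Laboratory Evaluations) plans three outputs that depend on a threshold:

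- Shift tables in a 3-by-3 low-normal-high layout, which "will be provided to assess changes in laboratory values from baseline to post-baseline visits".
- An abnormal-value count: "A summary of counts of subjects with an abnormal laboratory value at any visit including unscheduled will also be provided".
- Subjects with ALT or AST at or above 3 x ULN together with total bilirubin above 2 x ULN, who "according to Hy's Law will be listed".

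None of these has its own rule for two records at one visit. SAP 7.1 keeps unscheduled visits out of summaries, "except for the derivation of baseline and the summary of subjects with an abnormal laboratory value".

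Elsewhere the SAP does give worst-value rules. For MIC: "If there are multiple assessments collected for MIC assessment for one visit, the maximum MIC value will be used". For audiology, SAP 12.12 takes the highest CTC grade after baseline, unscheduled visits included.

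**The concern.** An average suits a table of means. It does not suit a table that asks whether a result crossed a limit. If an out-of-range result and an in-range repeat carry the same visit label, the mean can fall within range, and the shift table then shows a normal visit. The distortion runs towards normal.

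If repeats are often taken because the first result was abnormal, the rule acts mostly on the visits of interest. The documents do not say why repeats are taken. Their wording covers any reason, so confirmatory repeats are included.

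Adverse-event tables would not always recover such a result. Protocol 9.9.2 says laboratory abnormalities are usually not recorded as adverse events, except for findings such as those that are clinically significant, symptomatic, in need of intervention, or a cause of stopping study drug. With 50 subjects planned per arm (SAP 4.3.1), one subject in the wrong cell is 1/50 = 2 percentage points.

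**Working it through.** The plan gives no figure to reproduce. The check has two parts: which tables the averaging rule reaches, and which results it can hide.

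**Reach of the rule**

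1. *Shift tables.* These are summary tables and 12.9 states no exception, so the 7.6.4 default applies.
2. *Abnormal-value count.* Both 7.1 and 12.9 call this output a summary, which points to the 7.6.4 default. But 12.9 counts subjects with an abnormal value at any visit, and Protocol 10.7.4 has out-of-range values flagged without mentioning averaging. That points to individual values. Two programmers could both follow the SAP and report different counts.
3. *Hy's Law cases.* These are listed, and 7.6.4 averages only for summary tables. Nothing says that averaged values are screened.

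**How two records come to share a visit label**

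1. Two records are entered under the same visit.
2. SAP 7.6.5 moves an assessment to another visit when its date matches that visit's date.
3. SAP 7.6.5 also re-labels the EOT and EOS visits of subjects who leave the study early, as (visit date - randomization date)/28 rounded to the nearest month. For illustration, an early EOT 90 days after randomization gives 90/28 = 3.2, so Month 3. If the scheduled Month 3 visit took place at 84 days (84/28 = 3.0), both sets of results carry the Month 3 label.

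A repeat that keeps an unscheduled label is outside all three routes. It is not averaged with the scheduled result.

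**Arithmetic** (all laboratory values are assumed; the documents give none)

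Let the original be x and one repeat be r, both in multiples of ULN, with high meaning above 1. The value classified is (x + r)/2. The high result is hidden when (x + r)/2 <= 1, that is, when x <= 2 - r.

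| Repeat r | Largest original hidden, 2 - r |
|---|---|
| 0.5 | 1.5 |
| 0.6 | 1.4 |
| 0.7 | 1.3 |
| 0.8 | 1.2 |
| 0.9 | 1.1 |

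- Hidden: (1.3 + 0.6)/2 = 0.95 and (1.2 + 0.7)/2 = 0.95.
- With two repeats at 0.8, the limit is 3 - 2 x 0.8 = 1.4.
- Not hidden: (2.0 + 0.8)/2 = 1.40; (3.5 + 0.9)/2 = 2.20; (5.0 + 0.9)/2 = 2.95. All shrink but stay high.

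Classifying the most extreme record instead gives 1.3 and 1.2 for the two hidden pairs, both high.

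**The case against.** The case for leaving the text alone has real strength.

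- *The ordinary recheck may never be averaged.* Under 7.1, a repeat recorded as an unscheduled visit stays out of the shift table and enters the abnormal-value count as a separate record. The scheduled abnormal result stays where it was. This stands, and it limits the problem to records that share a label.
- *A local recheck does not dilute a central result,* because 7.6.4 reports the central one. This stands.
- *Nothing is lost from the data.* Individual values are listed. Nephrotoxicity as an event of special interest is identified from adverse-event preferred terms (SAP 12.5 and Appendix H), not from averaged laboratory values. This stands.
- *The tables are descriptive.* True, but a descriptive safety table should still classify results correctly.
- *The MIC rule is a weak parallel,* since only high MIC values matter there, whereas laboratory ranges have two sides. Fair. The audiology rule has the same one-sided character. Both show only that the SAP states a worst-value rule where it wants one.

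Two stronger readings are tempting. A reader might infer that the any-visit abnormal count is certainly built on averages. The SAP does not say so, and the wording of 12.9 fits individual values at least as well. A reader might also infer that Hy's Law cases could be missed. With a repeat of 0.9 x ULN, averaging would bring any original below 6 - 0.9 = 5.1 x ULN under the 3 x ULN limit. But that output is a listing, and 7.6.4 does not average for listings.

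**Conclusion.** The point holds in a limited form. As written, the SAP averages same-label laboratory repeats before they reach the shift tables, and this can classify a modest out-of-range result as normal. For the abnormal-value count, the defect is ambiguity, not a stated error.

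The effect is probably small. With one repeat between 0.5 and 0.9 x ULN, only originals up to 1.5 to 1.1 x ULN are hidden, and only when both records share a label. The 2 percentage points per subject is the weight of one misclassified subject. It is not an estimate of how many there would be, which the documents do not allow. For the any-visit count, a subject would drop out only if averages were used and that subject had no other abnormal value at any visit.

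**What to change.** Add to SAP 12.9:

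- Averaging under 7.6.4 applies only to descriptive statistics and change from baseline.
- Abnormal-value counts and Hy's Law screening use individual values.
- Post-baseline shift categories use the most extreme individual value at the visit. If one visit has both a low and a high value, show separate shift-to-low and shift-to-high displays, or add a low-and-high category. Placing the subject in two cells of the 3-by-3 table would stop the cells summing to n.

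The cost is a few lines of text and minor programming, with no new data. Abnormality counts may rise slightly.
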